6.5 Analysis for in-hospital all-cause mortality (secondary outcome)

For the analysis of in-hospital all-cause mortality, we will use a similar analysis strategy and similar models to the primary outcomes.

The raw percentage of in-hospital all-cause mortality will be summarized as n (%) by wedge and cycles (**Table 9**) and by intervention and control (**Table 9.1**).

Repeat model 1 to model 4 for in-hospital all-cause mortality, the resulting odds ratios (or coefficients) of all the fixed effects from Model 1 to Model 3 (unadjusted and adjusted), as well as their 95% CIs, will be reported along with their respective p-values in **Tables 10-12**.

6.6 Analysis for the composite score of KPIs (secondary outcome)

Based on 15 pre-defined binary KPIs, except for the length of stay, we will develop a composite score by simply sum up them with giving each KPI one score, and then normalize the score by dividing the sum by the number of eligible KPIs to the specific patient.

A simple description for the composite score by wedges and by cycles will be presented in **Table 17** (similar format to Table 5) and by intervention and control in **Table 13.1**.

Model 1 to model 4 (unadjusted and adjusted) will be applied to the composite score except that linear regression with GEE will be used instead of logistic regression with GEE for all the model analyses.

In a similar format to Table 6 to Table 8, the results of all the fixed effects from Model 1 to Model 3 (unadjusted and adjusted) for the composite score will be presented in **Table 14 to Table 16**, in which the regression coefficients will be also reported along with the odds ratios.

6.7 Analysis for 16 KPIs (secondary outcomes)

We will conduct similar descriptive analyses and apply model 1 and 2 to 16 KPIs. For 15 binary KPIs, logistic regression with GEE model will be used and odds ratios will be reported, and for the continuous KPIs, linear regression with GEE will be used instead of logistic regression with GEE and the regression coefficients will be reported instead of odds ratios.

A simple description for 16 KPIs by wedges and by cycles will be presented separately in **Table 17 to Table 32** (similar format to Table 5). And the simple description of them by intervention and control will be presented separately in **Table 17.1 to Table 32.1** (similar format to Table 5.1).

In a similar format to Table 6 and Table 7, the results from Model 1 and Model 2 (unadjusted and adjusted analysis) for each KPI will be presented as **Table 33 to Table 64**.

6.8 Analysis for a composite endpoint of MACE and re-hospitalization due to cardiovascular disease within 6-month after discharge (secondary outcome)

When performing the analysis for this endpoint, the follow-up rate (**Table 65**) will be examined. Should this exceed 10%, comparison between those followed up and those lost to follow up will be investigated. We will use Student's t test or chi-square to compare the baseline characteristics of ACS patients who completed the 6-month follow-up (completers) and those who did not (non-completers) because of withdrawal or loss-to-follow-up (**Table 66**).

A simple description for 6-month follow-up endpoint by wedges and by cycles will be presented in **Table 67** (similar format to Table 5) and that by intervention and control in **Table 67.1**.

Model 1 to Model 4 (unadjusted and adjusted) will be applied. Similar to Table 6 to Table 8, the resulting odds ratios of all the fixed effects from the Model 1 to Model 3 (unadjusted and adjusted) for 6-month follow-up endpoint, as well as their 95% CIs, will be reported along with their respective p-values in **Table 68 to Table 70**.

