6.1 Analysis Principles

The analyses will be conducted by intention-to-treat. All statistical tests will be two-tailed. Treatment effect for the primary and secondary outcomes will be considered significant at $\alpha=0.05$. We will not adjust for **multiplicity**.

We will not impute values unless specified otherwise. We will report the number of observations used in each analysis. Summaries of continuous variables that are normally distributed will be presented as means and SDs and skewed data will be presented as medians and inter-quartile intervals. Categorical variables will be presented as frequencies and percentages.

All analyses on outcomes will be at individual level but account for the clustering of patients in the same hospitals using appropriate statistical models. And except for model 1, all models will be adjusted for time (i.e. "6-month cycle").

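### The 6-month attrition check (SAP 6.8) puts its 10% trigger on follow-up instead of loss, ignores hospital clustering, and does not split Table 66 by intervention and control

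*SAP*

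**What the plan says.** SAP Section 6.8 covers the composite of MACE and cardiovascular re-hospitalisation within 6 months of discharge.

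- **Trigger.** It begins: "When performing the analysis for this endpoint, the follow-up rate (Table 65) will be examined". The next sentence is the rule: "Should this exceed 10%, comparison between those followed up and those lost to follow up will be investigated". The only thing that the pronoun can refer to is the follow-up rate.
- **Tests.** "We will use Student's t test or chi-square to compare the baseline characteristics" of completers and non-completers (Table 66). No adjustment for hospital is stated.
- **Groups.** Table 66 has no stated split by intervention/control, wedge or cycle. The endpoint itself is described by wedge and cycle (Table 67) and by intervention and control (Table 67.1).
- **Consequence.** No action is attached to the result of Table 66. Section 6.1 does not impute unless this is specified, and 6.8 specifies nothing. The sensitivity analyses in 6.10 cover the primary outcome, in-hospital death and the KPI score, but not this endpoint.

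Elsewhere, Section 6.1 requires outcome analyses to "account for the clustering of patients in the same hospitals using appropriate statistical models", and Section 6.3 compares baseline characteristics among wedges by GEE because patients cluster within hospitals.

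**The concern.** A threshold on the wrong quantity leaves the analyst to guess. At 92% follow-up, for example, the literal rule calls for Table 66 and the probable intended rule does not, and the choice would be made with the rates already known.

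Section 5 has hospital staff carry out the follow-up, so completion is likely to vary by hospital. Tests that treat patients as independent will then give P values that are too small.

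The same hospitals deliver the intervention, which includes patient education. It is therefore plausible that different kinds of patient are lost under intervention and under control. A single pooled comparison is not built to show that. At stake is how far a reader can trust the unadjusted 6-month odds ratio.

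**Working it through.** **1. The trigger.** The 10% is a rule with no derivation to reproduce. Loss = 100% − follow-up, so the two readings compare as follows.

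| Follow-up | Loss | As written (follow-up > 10%) | Read as loss > 10% |
|---|---|---|---|
| 90% to 100% | 0% to 10% | compare | do not compare |
| above 10%, below 90% | above 10%, below 90% | compare | compare |
| 10% or less | 90% or more | do not compare | compare |

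The readings disagree in the top and bottom rows. In practice the written rule is always met.

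**2. Clustering.** Inputs from the SAP: 25,000 patients and 104 hospitals (Section 2), giving 25,000/104 ≈ 240 per hospital; two-sided α = 0.05 (Section 6.1). Assumed: intra-class correlations (ICCs) of the baseline variable (ρx) and of loss (ρy). The SAP gives neither; its 0.10 in Section 4 is for the primary outcome.

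If the variable and loss both cluster by hospital but are unrelated, the variance is inflated by 1 + 239·ρx·ρy, and the true type I error is 2·[1 − Φ(1.96/√inflation)]. A simulation (2,000 trials per setting, 104 × 240 patients, trait prevalence 30%, loss 10%, plain chi-square) gives the last column.

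| ρx | ρy | Inflation | Type I error, formula | Simulated |
|---|---|---|---|---|
| 0.02 | 0.02 | 1.10 | 6.1% | 5.0% |
| 0.02 | 0.10 | 1.48 | 10.7% | 10.6% |
| 0.05 | 0.05 | 1.60 | 12.1% | 11.7% |
| 0.05 | 0.10 | 2.20 | 18.6% | 17.6% |
| 0.10 | 0.10 | 3.39 | 28.7% | 27.4% |

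Only patients discharged alive are followed up, so the true number per hospital is slightly below 240.

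**3. Pooling.** Assumed: 12,500 patients per condition (intervention, control), half high-risk (6-month event risk 20%) and half low-risk (10%), and no intervention effect (true OR 1.00). Loss is given as high-risk/low-risk. The chi-square compares risk group between lost and retained patients.

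| Case | Loss, control | Loss, intervention | Pooled chi-square | Observed OR |
|---|---|---|---|---|
| a | 15%/5% | 5%/15% | 0.0 (p = 1.0) | 1.045 |
| b | 10%/10% | 15%/5% | 174 (p < 0.001) | 0.978 |
| c | 15%/5% | 15%/5% | 694 (p < 0.001) | 1.00 |
| d | 5%/5% | 15%/15% | 0.0 (p = 1.0) | 1.00 |

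For case a, the observed control risk is (0.85·0.20 + 0.95·0.10)/1.80 = 0.1472 and the observed intervention risk is (0.95·0.20 + 0.85·0.10)/1.80 = 0.1528, so OR = (0.1528/0.8472)/(0.1472/0.8528) = 1.045. Within each condition the chi-square is 347, so a split would show at once what the pooled table hides.

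Case a is biased and missed. Case b is biased and flagged, but the pooled table cannot tell it from case c, which is unbiased. Case d has unequal loss rates and no bias. What matters is whether the type of patient lost differs between conditions, not the loss rates alone.

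**The case against.** - **A reader might infer that the check cannot detect bias at all.** The document does not support that. A trigger that is nearly always met only makes the comparison run every time. Ignoring clustering makes the tests flag too often, not too rarely. Only the missing split weakens detection, and case b shows that pooled data can still flag one-sided selection.
- **A reader might infer that Table 66 is the only protection for this endpoint.** It is not. Section 6.8 applies Models 1 to 4 unadjusted and adjusted, and Section 6.4 defines the adjusted analysis with patient- or hospital-level covariates. If loss depends only on variables in the model, a complete-case adjusted analysis is valid; in cases a and b, the OR within each risk group is 1.00. But adjusted analyses are labelled secondary, and their covariates are chosen by significance or clinical importance for the outcome, not for loss.
- **Loss by condition may be visible elsewhere.** Section 6.1 promises the number of observations in each analysis, Tables 67 and 67.1 split the endpoint, and the layout of Table 65 is not given. This could show unequal loss rates, but not which patients were lost.
- **Section 6.3 is not the same comparison.** Wedge is fixed by hospital and takes the full design effect, while completion varies within hospitals, so inflation depends on a product of two ICCs. The clustering rule in 6.1 is also worded for outcomes. Both remarks are fair. They limit the size of the error but do not justify dropping the adjustment.
- **The trigger is probably a slip for loss to follow-up.** Very likely, but the final SAP should state the rule that is meant.

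**Conclusion.** The point holds in three parts. The trigger is stated on the wrong quantity and screens nothing; this follows from the text without assumptions. The Table 66 tests ignore clustering that the SAP handles in its other baseline comparisons; the true type I error of a nominal 5% test runs from about 5–6% (both ICCs 0.02) to about 27–29% (both 0.10), so the size rests on ICCs that the SAP does not give. The comparison is not split by intervention and control, so it cannot show whether the type of patient lost differs between them.

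The consequence is moderate. Under strong assumed selection (15% against 5% loss) the unadjusted OR moves from 1.00 to 1.045 or 0.978. Only this secondary endpoint is affected; the in-hospital primary outcome is not.

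**What to change.** In Section 6.8:

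1. State the trigger as loss to follow-up above 10%, or drop it and always report the comparison.
2. Report loss by intervention/control, wedge and cycle in Table 65.
3. Do the Table 66 comparison by GEE with clustering by hospital: each baseline characteristic regressed on completion, intervention, their interaction, and cycle. The interaction is what would reveal case a. A model of completion on intervention and cycle alone would not, because loss is 10% in both conditions there; it would instead flag case d, where there is no bias.
4. If a weighted sensitivity analysis of the 6-month Model 2 is added, put intervention-by-covariate interactions in the follow-up model. In case a, a main-effects model gives every patient the same weight (retention 90% by risk group and by condition) and leaves the OR at 1.045.

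The cost is a change of SAP wording and a little extra analysis. No new data are needed.

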6.9 Intra-cluster coefficient for outcomes

The **Intra-cluster coefficient (ICC)** for primary outcome and all the secondary outcomes will be estimated from all periods' data. (**Table 71**)

6.10 Sensitivity analyses

During the study operation and data management, the study team developed two indices: a **quality index and an intervention index**. The quality index is based on the clinical research associates (CRAs) evaluation of the study performance of each hospital (the percentage of data items that could not be verified for CRA reviewed cases).

We will repeat the above descriptive analyses and Model 2 for the primary outcome and the two secondary outcomes (in-hospital total death and the composite score of KPIs), after excluding those hospitals with poor data quality and compare the results with the main analyses to help us to draw final conclusions.

The simple description for primary outcome by wedges and by cycles after excluded hospitals with poor quality of data will be presented in **Table 72** (similar to Table 5) and by intervention and control in **Table 72.1**.

The results of model 2 (unadjusted and adjusted) for primary outcome after excluding hospitals with poor quality of data will be presented in **Table 73**, similar to **Table 7**.

The simple description for in-hospital all-cause mortality by wedges and by cycles after excluded hospitals with poor quality of data will be presented in **Table 74** (similar to Table 9) and by intervention and control in **Table 74.1**.

The results of model 2 (unadjusted and adjusted) for in-hospital all-cause mortality after excluding hospitals with poor quality of data will be presented in **Table 75**, similar to Table 11.

The simple description for the composite score of KPIs by wedges and by cycles after excluded hospitals with poor quality of data will be presented in **Table 76** (similar to Table 13) and by intervention and control in **Table 76.1**.

The results of model 2 (unadjusted and adjusted) for the composite scores after excluding hospitals with poor quality of data will be presented as **Table 77**, similar to Table 15.

During the site monitoring, our CRAs recorded 6 evaluation fields, from each hospital, about how well each intervention was implemented. An intervention index was made based on these field notes to objectively evaluate the implementation and completion of intervention.

The results of Model 2 analysis (unadjusted and adjusted) for in-hospital MACE when further adjusted the intervention index will be presented in **Table 78**, similar to table 7.

